Anatomical and spectroscopic images (T1, T2, ¹H-MRS) will be acquired using the Center for Biomedical Imaging at MUSC's standard imaging protocols. The T1 and T2 images will be used for the computation of stroke lesion locations and volumes. The T1 images will also be used to guide the corticomotor response (CMR) testing listed below. We will use Single-voxel MEGhcher-GArwood Point RESolved Spectroscopy (MEGA-PRESS) ¹H-MRS to assess central nervous system inflammation. Voxels will be placed in the basal ganglia and insular cortex in both hemispheres. Basal ganglia voxels will be placed with the anterior border abutting the anterior portion of the lentiform nucleus and as medial as possible to avoid the ventricles (Pretzsch et al. 2019). The basal ganglia have been previously implicated in fatigue post-stroke (Tang et al. 2010) and in multiple sclerosis (Roelcke et al. 1997, Tellez et al. 2008). The insular cortex is a prominent brain region involved in interoception. Interoception is the sensing, integrating, interpreting and regulating self-signals and has been theorized to contribute to fatigue (Stephan et al. 2016, Enoka et al. 2021) and implicated in fatigue in multiple sclerosis (Gonzalez Campo et al. 2020). Levels of Myo-inositol (MI), total creatine (tCr), and choline (CHO) and their ratios to N-acetylaspartate (NAA) will be quantified as markers of inflammation (reviewed by Chang et al. 2015). Spectroscopy data will be analyzed using the freely available LCModel software as in our previous works (Moss et al. 2018, 2019). Pre and post tDCS intervention spectroscopy values will be compared to determine changes in inflammatory markers associated with the intervention. The measurement of state fatigue will be performed before and after each imaging session.

Blood collection and analysis

Before and after five days of tDCS treatment, participants will provide a blood sample for the measurement of pro-inflammatory cytokines. These cytokines include interleukin- (IL) 1, 6, and 10, tumor necrosis factor (TNF) α , and c-reactive protein. Whole blood will be collected in EDTA-treated tubes and separated into plasma, immune cells (buffy coat), and red blood cells. Separated samples will be frozen and stored until the end of the study. Once all samples are collected they will undergo Simple Plex™ microfluidic ELLA platform immunoassay (ProteinSimple, USA) analysis for listed cytokines (Leligdowicz et al. 2017, Burke et al. 2021). State fatigue will

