
Table 1: Clinical Outcome Measures

Domain	Instrument
Fatigue (State)	Visual Analogue Scale
Fatigue (Trait)	* Fatigue Severity Scale (FSS) (Krupp et al. 1989) Modified Fatigue Impact Scale (mFIS) (Fisk et al. 1994) Fatigue Assessment Scale (FAS) (Michielsen et al. 2003)
Anxiety	Hospital Anxiety and Depression Scale (Zigmond and Snaith 1983)
Depression	Patient Health Questionnaire 9 (PHQ-9) (Spitzer and Williams 1999)
Pain	Defense and Veterans Pain Rating Scale (DVPRS) (Polomano et al. 2016)
Physical Function / Mobility	10 m walk over GAITRite (Kindred et al. 2019)
Community Participation / Quality of Life	Standard Form 36 (Anderson et al. 1996)

* Primary outcome measure for Aim 1

Statistical Analysis

Aim 1 Hypothesis: Five days of a-tDCS applied to the lower extremity motor cortex will result in a reduction of PSF severity in individuals with chronic stroke. A two-factor, between-subjects factor of GROUP (active a-tDCS, sham) and within-subjects factor of TIMEPOINT (pre, post), mixed model ANOVA will be used to test this hypothesis. The primary outcome variable for this analysis is the FSS scores. We will also calculate measures of effect size to power future studies.

Aim 2 Hypothesis: Five days of a-tDCS applied to the lower extremity motor cortex will result in a reduction of inflammatory markers within the central nervous system and the peripheral blood. Pre- and post-intervention markers of inflammation will be compared using a mixed model, two-factor ((between-subjects factor of GROUP (active a-tDCS, sham) and within-subjects factor of TIMEPOINT (pre, post)), ANOVA. Each outcome measure (MI, tCR, IL-1, TNF- α , etc) will be tested independently.

Additional Analyses: Examine the possible relationship between PSF severity and inflammatory markers. This relationship may provide mechanistic insight into the effect of tDCS on PSF and allow us to possibly predict future responders/non-responders to a-tDCS treatments of PSF. Pearson's correlations will be calculated between baseline measures of inflammation and FSS scores to determine a possible role of current state inflammation on PSF severity. Correlations between the change in FSS scores and inflammation, pre- and post-a-tDCS, will be calculated to provide preliminary evidence of a possible mechanism of reduced inflammation and improved PSF.

Potential Problems / Solutions

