Research staff will search RESTORE for potential research participants and make initial contact via phone. Research staff will also respond to inquiries received from the community via phone. The research activities will be explained to prospective participants by the research staff. If the prospective participants express interest in partaking in the study they will be invited to the laboratory to confirm eligibility and provide written consent.

Retention

Enrolled participants will receive \$100 USD as remuneration for their participation in the proposed study. Remuneration will be delivered by pre-paid debit-type card that will be loaded at pre-determined milestones (after initial MRI, after each (5) treatment visit, after follow-up phone calls.

RISKS TO HUMAN PARTICIPANTS

[name] (PI) will be performing the proposed intervention at the College of Health Professions Research building on the Medical University of South Carolina campus. The research building is staffed with licensed clinical professions, physical and occupational therapists, and all research staff are trained in emergency procedures. Research staff also have basic life support (BLS) training from the American Red Cross, or equivalent. All investigators and research staff have completed computer-based CITI Human Subjects Research ethical and safety training, as required by the Medical University of South Carolina and the associated IRB. All research activity, informed consents, and continuing reviews will be reviewed by MUSC's IRB, before the research is started and continuing reviews will occur annually. The research staff will ensure that all information needed for the continuing reviews are available to the IRB in accordance with the IRB's requirements.

Human Subjects Involvement and Characteristics and Design

A total of 24 adults, between 35 and 80 years of age, with unilateral strokes more than 6 months post event will be recruited and enrolled over a one year period. The proposed randomized, single-blind, sham-controlled, trial will investigate the effects of anodal transcranial direct current stimulation (tDCS) on post-stroke fatigue and markers of inflammation. Participants will be randomly assigned to the active a-tDCS or sham group. Clinical and inflammatory markers will be assessed pre and post five consecutive days of a-tDCS applied to the motor cortex.

The inclusion/exclusion criteria for the study are as follows:

Inclusion Criteria:

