1. Men and Women, any race or ethnicity, ages 35-80 years
2. 6+ months post-stroke
3. Average Fatigue Severity Score (FSS) ≥ 4 (indicates clinically significant fatigue)
4. Self-reports persistent fatigue for at least the past 6 months
5. Able to walk 10m unassisted

Exclusion Criteria:

1. Absolute contraindications to MRI, TMS, tDCS
2. Inability to follow 3-step instructions
3. Multiple strokes on opposite hemispheres
4. Diagnosis of comorbid neurological conditions (e.g. multiple sclerosis, Parkinson's disease, and dementia)
5. Severe hypertension (resting SBP > 200 mmHg or DBP > 120)
6. Cerebellar or brainstem strokes
7. Hospital Anxiety and Depression Scale (HADS) score > 7 , depression or anxiety
8. Pregnancy

Study Procedures, Materials, and Potential Risks

Source of Materials

Data will be in the form of structured interviews, self-reported rating scales and questionnaires, surface electromyography recorded transcranial magnetic (TMS) evoked potentials, and MRIs. No identifiable information is expected to be collected outside of the consent process. Once consented individuals will be assigned a non-identifiable research ID number that will be used to mark/track collected data.

Research Procedures and Potential Risks

Although unlikely, it is possible that some participants may experience distress when asked questions pertaining to their feelings of fatigue, depression, anxiety, or pain. Some participants may also experience

distress during MRI sessions or TMS assessments. However, previous and ongoing research by our research group indicates that these risks are minimal.

Specific risks, which are all low/minimal, associated with the research procedures are as follows:

tDCS: Commonly reported side effects are as follows: local skin irritation with light itching/tingling/ burning, mild headache, or nausea. There have also been rare cases of mild burns at the procedure site.

TMS: There is a very low risk of a seizure after TMS. The risk of seizure induction by this protocol has been thoroughly assessed and the TMS parameters have been chosen to be well within published safety guidelines for the conduct of TMS studies in human subjects.

Blood Draw / Venipuncture: Risks associated with blood draws include momentary discomfort and/or bruising. Infection, excess bleeding, clotting, or fainting is possible, although unlikely.

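### The exploratory baseline correlation of MRS markers with FSS makes no stated use of the lesion maps, so infarct inside an ipsilesional voxel can dilute it or be read as inflammation

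*Combined protocol and SAP*

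**What the plan says.** Under Neuroimaging, "Voxels will be placed in the basal ganglia and insular cortex in both hemispheres", which gives four voxels per person. The only placement rule concerns the basal ganglia and is anatomical: the voxel sits "as medial as possible to avoid the ventricles". No rule is given for the insula. Myo-inositol, total creatine, choline and "their ratios to N-acetylaspartate (NAA) will be quantified as markers of inflammation".

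The same section says that "The T1 and T2 images will be used for the computation of stroke lesion locations and volumes". No later section ties these lesion data to the spectroscopy, whether as a placement rule, a reason to drop a voxel, a tissue correction, a covariate or a stratum.

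The population is "A total of 24 adults, between 35 and 80 years of age, with unilateral strokes more than 6 months post event" (Human Subjects Involvement and Characteristics and Design). The exclusion list removes "Cerebellar or brainstem strokes" and "Multiple strokes on opposite hemispheres". Infarcts of the basal ganglia or insula remain eligible, and each participant should have one lesioned and one unlesioned hemisphere.

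Under Additional Analyses in the Statistical Analysis section, Pearson "correlations will be calculated between baseline measures of inflammation and FSS scores", with the result taken as evidence on whether inflammation has a role in fatigue severity. There is no lesion or hemisphere term, and the plan does not say how values from the two sides are combined. Potential Problems / Solutions names the choice of brain region as an MRS limitation but does not mention infarct in the voxel.

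**The concern.** A voxel that is partly infarct measures lost or altered tissue as well as whatever inflammation is present. Metabolite levels and NAA ratios can therefore differ between two people only because one person's lesion reaches the voxel. The baseline correlation compares people with one another, so such differences do not cancel.

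Two errors are possible. If overlap is unrelated to fatigue, it adds noise to the marker and weakens a true correlation. If infarct at that site also goes with higher or lower FSS, it confounds the correlation, and a lesion effect could be reported as an inflammatory one. The plan's own rationale makes the second path plausible: it supports the choice of the basal ganglia by citing an MRI study of acute basal ganglia infarcts in post-stroke fatigue.

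What is at stake is the mechanistic reading. The plan hopes these correlations will give mechanistic insight and may help to predict responders, and the Innovation section looks ahead to an inflammation-based phenotype for later trials.

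**Working it through.** **No figure to reproduce.** The plan gives no SD, effect size, power or expected lesion overlap for any MRS marker. Its 80% power statement concerns FSS only. From the documents come n = 24, alpha = 0.05, four voxels per person and the unadjusted Pearson correlation. Everything else below is assumed, as are two-sided testing and a true correlation of 0.5 between inflammation and FSS.

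**Step 1: model.** Let marker = inflammation (SD 1) + D × (infarct in voxel), where a share p of participants have infarct in that voxel and D is the shift in SD units. The lesion-related variance is p(1−p)D².

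- Lesion share of marker variance = p(1−p)D² / [1 + p(1−p)D²]
- Observed r, if infarct is unrelated to FSS = 0.5 / √[1 + p(1−p)D²] = 0.5 × √(1 − share)

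**Step 2: dilution.** Example at p = 0.25, D = 2: p(1−p)D² = 0.1875 × 4 = 0.75; share = 0.75/1.75 = 43%; r = 0.5/√1.75 = 0.38. Power is simulated at n = 24, two-sided 0.05.

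| Assumption | Lesion share | Observed r | Power, unadjusted |
|---|---|---|---|
| no infarct effect | 0% | 0.50 | 0.73 |
| p = 0.10, D = 0.5 | 2% | 0.495 | not run |
| p = 0.10, D = 1 | 8% | 0.48 | 0.69 |
| p = 0.25, D = 1 | 16% | 0.46 | 0.64 |
| share set directly | 25% | 0.43 | 0.58 |
| p = 0.25, D = 2 | 43% | 0.38 | 0.46 |
| share set directly | 50% | 0.35 | 0.41 |
| p = 0.25, D = 3 | 63% | 0.31 | 0.31 |
| share set directly | 75% | 0.25 | 0.22 |

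With overlap as a covariate, power is about 0.71 in every simulated p, D scenario.

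**Step 3: confounding.** Now let inflammation have no effect on FSS, and let infarct at the site shift FSS by g SD. The induced correlation is p(1−p)Dg / √{[1 + p(1−p)D²][1 + p(1−p)g²]}. At p = 0.25, D = 2, g = 1 this is 0.375/√(1.75 × 1.1875) = 0.26. Simulated false-positive rates at nominal 0.05, with D from 1 to 3:

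| p | g = 0 | g = 0.5 | g = 1 |
|---|---|---|---|
| 0.25 | 0.05 | 0.07 to 0.12 | 0.11 to 0.33 |
| 0.50 | 0.05 | 0.08 to 0.16 | 0.15 to 0.45 |

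Adjusting for overlap returns the rate to 0.048 to 0.053 throughout. The inflation appears only if infarct at the voxel site is itself related to FSS.

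**Step 4: the Aim 2 test.** If infarct adds the same amount D before and after treatment, the change is (post + D) − (pre + D) = post − pre. In simulation, the type I error of the group-by-time test was 0.052 with D = 0 and 0.048 with D = 3.

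**The case against.** The strongest reply is that this is a minor analysis. The correlation is listed as additional, in tentative wording, in a pilot whose primary outcome is FSS. It also includes blood markers, which voxel overlap cannot touch, and two of the four voxels are contralesional. Only people whose infarct reaches the basal ganglia or insula are exposed, and the documents do not say how many that is. All of this stands and sets the scope of the point.

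A reader might infer more in three ways:

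- **That the MRS results as a whole, including Aim 2, are contaminated.** The documents do not support this, since a stable additive shift drops out of the change. Repositioning of the voxel between scans, or ratios that do not behave additively, could leave some residue, but nothing in the documents gives it a size.
- **That the lesion data will certainly go unused.** The plan defers to the imaging centre's standard protocols and to an LCModel workflow from earlier work, either of which might include tissue correction. What can be said is that no use is described.
- **That the larger losses in the tables are expected.** They follow from assumed inputs. At the mild end the correlation barely moves, and false-positive inflation needs a link between infarct site and FSS that the trial has not shown.

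There is also a fair objection to adjustment. The plan itself says that stroke induces neuroinflammation. If the lesion causes inflammation and inflammation causes fatigue, conditioning on overlap removes part of the signal sought. This stands, and it is why the adjusted estimate should not replace the unadjusted one.

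**Conclusion.** The point holds as a low-cost improvement to one exploratory analysis. As written, the baseline correlation of ipsilesional MRS markers with FSS cannot separate inflammation from infarct in the voxel. The size is unknown. On assumed lesion shares of 2% to 75% and an assumed true r of 0.5, the observed r would lie between about 0.495 and 0.25. If infarct at the site shifts FSS by 0.5 to 1 SD, with p = 0.25 or 0.50 and D from 1 to 3, the false-positive rate would lie between 0.07 and 0.45; without that link it stays near 0.05. These figures show how the result depends on overlap and are not a forecast for this trial. Confidence in the mechanism is good; confidence in the magnitude is low.

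**What to change.** Add the following to the Neuroimaging and Additional Analyses text:

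1. Label every voxel ipsilesional or contralesional and analyse the two sides separately.
2. From the T1 and T2 images already acquired, compute the fraction of each voxel that lies inside the lesion mask, and report its distribution.
3. Report each ipsilesional baseline correlation with FSS both unadjusted and adjusted for the overlap fraction, with the contralesional correlation as the lesion-free comparison.
4. If voxels above some overlap are to be left out, fix the limit before marker and FSS data are examined together. Tying it to unblinding would not protect this analysis, which does not use treatment arm.

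The cost is a little image processing, one covariate and possibly some lost ipsilesional values; how many depends on the overlap found. If infarct turns out not to matter, the covariate costs little: simulated power at a true r of 0.5 goes from 0.73 to about 0.71. The adjusted estimate may remove part of any inflammation caused by the lesion, so a gap between the two estimates should be reported as unresolved rather than settled in favour of either. No extra visits, scans or participants are needed.

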This pilot proposal is a randomized longitudinal single-blind sham-controlled intervention. Individuals with PSF will be randomly assigned to the sham or a-tDCS treatment group. Before and after five consecutive days of a-tDCS applied bilaterally over the left and right lower extremity motor cortex, PSF and nervous system and peripheral inflammation will be measured, similar to De Doncker et al. (2021). The tDCS treatment will consist of twenty minutes of 4 mA a-tDCS delivered via two carbon rubber electrodes placed inside sponge pads (1x1 tDCS, Soterix, USA). The current will be ramped up 4 mA over 30 seconds. Each electrode has a surface area of 70 cm², resulting in a current density of 0.06 mA/cm² and a charge density of 1.1 C/cm², which are within current safety guidelines (Bikson et al. 2016). The anode electrode will be centered on the interhemispheric fissure and the central sulcus. This area was chosen due to its previous use in fatigue studies using neuromodulation (multiple sclerosis, Ferrucci et al. 2014; fibromyalgia, Altas et al. 2019; Stroke, De Doncker et al. 2021). The motor cortex is being used more often in neuromodulation studies due to its structural and functional connectivity to cortical and subcortical networks/nodes, e.g. basal ganglia, cingulate cortex. The cathodal electrode will be placed on the nonparetic shoulder. Modeling of cephalic and extracephalic tDCS montages indicates that extracephalic placement of the cathode leads to deeper current flow in the somatosensory cortex (Noetscher et al. 2014). The sham tDCS procedure will be performed in the same manner as active a-tDCS, however, the current will be ramped up and down over 30 seconds (Fridricksson et al. 2018). Figure 2 displays the protocol timeline. Days 2-6 will be consecutive, no more than 36 hours will be allowed between treatment visits. If more than 36 hours elapses the participant will be withdrawn from the study. The measurement of state fatigue, via f-VAS, will be performed before and after each tDCS treatment visit. Follow-up assessments of state and trait fatigue will be performed via phone at one (Follow-up 1), two (Follow-up 2), and four weeks post-treatment (Follow-up 3). The primary study outcome will be the comparison of the FSS scores obtain at baseline (Visit 1) and one week post-tDCS (Follow-up 1).

Neuroimaging

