Some groups have reported a 50% response rate to tDCS. Due to our small sample, non-responders may reduce our statistical power. A post-hoc response analysis, defined as a change greater than the minimally clinically important difference of 0.45 (Nordin et al. 2016), will be performed to power future studies. Placing the ¹H-MRS voxel within the basal ganglia is a logical starting place based on the published literature. However, it is possible that inflammatory markers outside this region are as influential or more so than basal ganglia measures. Future work may be required to determine which brain regions are best to assess with ¹H-MRS. Another limitation is that only a-tDCS is being tested. Cathodal tDCS (c-tDCS) has been reported to have similar long-term effects on gene expression and protein synthesis. The benefits of tDCS on fatigue, to date, have mostly investigated a-tDCS although future investigations need to determine if c-tDCS may be a viable treatment option. Another area that will need to be addressed in future studies is if our post-intervention measurements of metabolite changes reflect the last episode of treatment or if they are indicative of long-term changes in response to tDCS. Future studies will also need to assess the optimal intervention length and follow-up periods.

Biostatistical Justification

This pilot work is based on a similar study investigating a-tDCS' effects on post-stroke fatigue (De Doncker et al. 2021). The FSS is the primary measure of fatigue severity and the minimally clinically important difference (MCID) was reported to be 0.45 (Nordin et al. 2016), with changes greater than this resulting in reported improvements in QOL. To detect this level of change with 80% power and an alpha = 0.05 between two groups using a within-between-subjects interaction ANOVA a minimum sample of 8 individuals in each group is required. We will enroll 24 participants (12 a-tDCS, 12 sham) to account for any drop-out, loss to follow-up, or complications during data collection. We have projected to perform recruitment and data collection activities over nine months.

REFERENCES

Altas, E. U., Askin, A., Besiroglu, L., & Tosun, A. (2019). Is high-frequency repetitive transcranial magnetic stimulation of the left primary motor cortex superior to the stimulation of the left dorsolateral prefrontal cortex in fibromyalgia syndrome? *Somatosens Mot Res*, 36(1), 56-62.

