The intervention being studied is a five-session anodal transcranial direct current stimulation (tDCS) intervention delivered over five consecutive days. Measures of post-stroke fatigue and inflammation (central inflammation measured by magnetic resonance spectroscopy and peripheral markers measured via blood analysis) will be made before and after the intervention.

Trial Management. The study will be primarily managed from the Functional Neurostimulation Laboratory ([name], PI) within the Division of Physical Therapy within the College of Health Professions at the Medical University of South Carolina. The target population is adults more than six months post-stroke with clinically present fatigue (average Fatigue Severity Scale > 4).

Data Management and Analysis

The primary outcome of the study is the change in post-stroke fatigue severity (fatigue severity scale (FSS), pre- and post-intervention) and markers of central (measured using magnetic resonance spectroscopy (MRS)) and peripheral (measured via blood analysis) inflammatory markers. Analyses will be guided by the specific hypotheses of the study. Post-hoc exploratory analyses will be conducted with two-tailed tests and more conservative statistical procedures which guard against Type I error (e.g., Tukey tests). All primary hypotheses will be tested at level of significance $\alpha=0.05$. We will also estimate the effect sizes of interest and provide 95% confidence intervals for them.

Quality Assurance

Data quality will be monitored by random inspection of the completed forms by research staff/PI.

Regulatory Issues. All unexpected Adverse Events (AEs) will be reported to the MUSC IRB within 10 working days. Serious AEs (SAEs) will be reported within 24-business hours. Follow-up of all unexpected and serious AEs will also be reported to the IRB. All AEs will be reviewed weekly by the PI and yearly by the IRB. Any significant actions taken by the local IRB and protocol changes will be relayed to NIH. AEs and SAEs occurring during the course of the trial will be collected, documented, and reported in accordance with IRB requirements.

Definition of AE and SAE

Adverse events are defined as any untoward medical occurrence that may present itself during treatment or administration of an intervention, and which may or may not have a causal relationship with the treatment.

Serious adverse events are defined as any medical occurrence that:

- Results in death,
- Is life-threatening,

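### The Aim 1 test is a t-test on FSS change without baseline adjustment; an ANCOVA on Visit 1 FSS would remove the shift caused by chance baseline imbalance, at a small precision cost if the baseline slope is near 1

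*Combined protocol and SAP*

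**What the plan says.** The Aim 1 paragraph of Statistical Analysis specifies the model: "A two-factor, between-subjects factor of GROUP (active a-tDCS, sham) and within-subjects factor of TIMEPOINT (pre, post), mixed model ANOVA will be used". Biostatistical Justification identifies the tested term as the interaction: "using a within-between-subjects interaction ANOVA a minimum sample of 8 individuals in each group is required". Study Design and a-tDCS Treatment fixes the two timepoints: "The primary study outcome will be the comparison of the FSS scores obtain at baseline (Visit 1) and one week post-tDCS (Follow-up 1". Data Management and Analysis describes the same quantity as a change: "The primary outcome of the study is the change in post-stroke fatigue severity".

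Visit 1 FSS therefore enters only as the pre level of the outcome, and no section names it as a covariate. Age is to be explored, and age, stroke date, sex and race/ethnicity are collected as possible influences, but none of these adjusts for baseline FSS. On allocation, the human-subjects section says only: "Participants will be randomly assigned to the active a-tDCS or sham group". No stratification or balancing on FSS is described.

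The estimate itself is a deliverable. Aim 1 says: "We will also calculate measures of effect size to power future studies". Data Management and Analysis adds: "We will also estimate the effect sizes of interest and provide 95% confidence intervals for them".

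**The concern.** A change score subtracts the whole of the baseline score. If participants with high Visit 1 scores tend to regress towards the mean, that subtraction is too large. The arm that happens to start more fatigued then appears to improve more, whatever the treatment does. Averaged over all possible randomisations this cancels, but it does not cancel in the one trial that will be run.

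With 8 to 12 per arm, the difference in baseline means has a standard deviation of 0.50 to 0.41 FSS SDs, so a visible imbalance would be unremarkable. The observed effect and its interval are meant to inform later trials, so an avoidable error in them would be carried forward. The Visit 1 scores needed to remove it are already collected.

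**Working it through.** **Inputs from the documents.** Difference of interest 0.45 FSS points (MCID), 80% power, alpha 0.05, minimum 8 per group, 24 enrolled as 12 + 12 (Biostatistical Justification). Entry requires "Average Fatigue Severity Score (FSS) ≥ 4 (indicates clinically significant fatigue" (Inclusion Criteria). **Not given:** FSS SD, SD of change, pre-post correlation or slope. These are assumed below and shown as ranges.

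**1. The plan's own figure.** Without an SD or correlation, 8 per group can be neither reproduced nor refuted. Solving backwards with the exact two-sided noncentral t (df 14), 80% power needs a standardised difference of 1.507, so the SD of change is 0.45 / 1.507 = 0.299. The same SD gives 94.1% power at 12 per arm. Planned-test power at larger SDs of change (8 / 12 per arm) is 45% / 63% at SD 0.46 and 29% / 42% at SD 0.6.

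**2. Identity of the tests.** In one simulated data set with 12 per arm, the interaction F and the squared t on change were both 3.50586 (df 22, p = 0.0745).

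**3. The shift.** Let D be the active-minus-sham difference in Visit 1 means, b the slope and T the treatment effect. Given D, the expected difference at Follow-up 1 is T + bD. The change-score estimate subtracts D, giving T - (1 - b)D. ANCOVA subtracts bD instead and leaves T.

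**4. Size with equal pre and post variances (b = r).** The SD of D is s x sqrt(2/n), and the SE of the change estimate is s x sqrt(2(1 - r)) x sqrt(2/n). A 1-SD imbalance therefore shifts the estimate by (1 - r)/sqrt(2(1 - r)) SE. At 12 per arm the SE is 0.2987 x sqrt(2/12) = 0.1219.

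| r | shift (SE) | FSS points | % of 0.45 | implied baseline SD |
|---|---|---|---|---|
| 0.5 | 0.500 | 0.061 | 13.5 | 0.30 |
| 0.7 | 0.387 | 0.047 | 10.5 | 0.39 |
| 0.8 | 0.316 | 0.039 | 8.6 | 0.47 |
| 0.9 | 0.224 | 0.027 | 6.1 | 0.67 |

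**5. Precision with equal variances.** The ANCOVA-to-change variance ratio is (1 + r)/2 x (1 + 1/(N - 4)). At N = 24 this is 0.75 x 1.05 = 0.79 at r = 0.5, 0.89 at 0.7 and 1.00 at 0.9. Break-even, (1 - r)/(1 + r) = 1/(N - 4), falls at r of about 0.90 for N = 24 and 0.85 for N = 16. At slope exactly 1, the simulated interval is 2.6% wider at 12 per arm and 4.5% wider at 8.

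**6. With the entry cut-off.** Baselines were simulated as normal (mean 4.5, SD 1.2, or mean 5.0, SD 1.0) truncated to 4-7, which leaves an SD of 0.72-0.73. The residual variance was SD²(1 - slope²) using the untruncated SD, with 60,000 trials per setting. Using the truncated SD for the residual instead makes the case for ANCOVA stronger.

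| slope | shift (SE) | CI ratio, 12 per arm | CI ratio, 8 per arm |
|---|---|---|---|
| 0.5 | 0.330-0.384 | 0.948-0.969 | 0.965-0.988 |
| 0.7 | 0.247-0.290 | 0.982-0.995 | 1.001-1.014 |
| 0.8 | 0.198-0.234 | 0.998-1.006 | 1.016-1.025 |
| 0.9 | 0.138-0.163 | 1.013-1.017 | 1.032-1.035 |

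CI ratios are ANCOVA over change score. Type I error at 12 per arm is about 5% overall for both methods. In the 16% of trials where one given arm starts most fatigued, it is 6.6-7.1% (slope 0.5) or 5.8-6.1% (slope 0.7) for change scores, and about 5% for ANCOVA.

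**7. Relative power.** With the effect rescaled so that the change-score test has 80% power at 8 per arm, ANCOVA has 81-83%, 79-80%, 78-79% and 77% at slopes 0.5, 0.7, 0.8 and 0.9. At 12 per arm, against 94%, it has about 96%, 94-95%, 94% and 94%. These figures compare the two methods; they are not power for 0.45 points.

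**The case against.** The strongest reply is that the plan contains no error here. The test is valid, the sections agree with one another, and the change score is a recognised choice.

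The magnitudes also come from different scenarios. The shifts in FSS points use an SD of change of 0.299, which at correlations 0.5 and 0.7 implies baseline SDs of only 0.30 and 0.39. The cut-off simulation has a baseline SD of 0.72-0.73 and SDs of change of roughly 0.44 to 1.10, at which planned power for 0.45 points at 8 per arm is far below 80%. If 0.299 is combined with that baseline SD, the slope must be high: about 0.915 with equal variances, or 0.955-0.969 in the simulation model. A 1-SD imbalance at 12 per arm then moves the estimate by 0.025 or 0.009-0.013 points respectively (under 6%, or 2-3%, of 0.45). In the simulation model ANCOVA widens the interval by about 2% at 12 per arm and 4% at 8, and power at 8 per arm falls from about 80% to 77%.

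All of that stands, and it is why no power gain is claimed. It does not undo the point. The 0.299 is back-calculated, not stated. If the real SD of change is larger, the shift can be larger too, though the stated power then fails, which is a separate matter. Across the range, the possible loss is a few per cent of interval width.

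Two practical remarks also stand: the sample-size text refers to the interaction ANOVA and would need aligning, and participants without a Follow-up 1 score need a stated rule.

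**Conclusion.** The point holds as an improvement to a valid test, not the repair of a broken one. The planned analysis is a change-score t-test with no Visit 1 covariate, and nothing in the allocation compensates. ANCOVA targets the same effect and removes the shift that goes with the observed baseline difference. For a 1-SD imbalance the shift is 0.22-0.50 SE with equal variances and correlations 0.9-0.5, or 0.14-0.38 SE with the assumed cut-off distributions and slopes 0.9-0.5. It is smaller still if the slope is nearer 1.

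This rests on complete pairs, on a linear slope common to both arms, and on slopes and SDs that the documents do not give. It concerns imbalance in measured FSS only. The justification is removal of conditional bias in a pilot estimate intended for reuse.

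**What to change.** In Statistical Analysis, make the primary Aim 1 analysis an ANCOVA of Follow-up 1 FSS on GROUP with Visit 1 FSS as covariate, and report the adjusted group difference with its 95% confidence interval. The outcome need not be redefined: an ANCOVA of FSS change with the same covariate gives the same adjusted difference and interval.

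State the ANCOVA explicitly. Adding Visit 1 FSS as a main effect to the 2x2 ANOVA does not achieve it. In one simulated data set the interaction estimate was -0.1334 with or without that term, while ANCOVA gave -0.2378.

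Align the wording of Biostatistical Justification with the new analysis, and say how a missing Follow-up 1 score is handled. The same model could be used for each Aim 2 marker, but no marker-specific gain was calculated, so that is optional.

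The cost is some SAP wording, one degree of freedom and the variance of an estimated slope. With the entry cut-off, the interval at 8 per arm is 0-1% wider at slope 0.7 and about 3% wider at 0.9. At 12 per arm a loss appears only from a slope of about 0.8 and is at most 2% up to slope 0.9. No new data are needed.
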